# **Risks and Benefits:**

- 1. **Screening:** Healthy control subjects (HCS) and schizophrenic subjects (SZS) will undergo a Structured Clinical Interview for DSM-IV conducted by a research assistant and a psychiatric evaluation by the research psychiatrist at the VA Hospital in West Haven. The diagnostic interviews may cover issues, which are stressful to a person, for example, questions regarding the experience of paranoid thoughts or social isolation. Thus, SZS may experience some distress of worsening of psychiatric symptoms.
- 2. **Loss of Confidentiality:** Participation in research may involve a loss of privacy and confidentiality. Therefore, extensive measures are in place to protect the confidentiality of subjects.
- 3. Treatment with PF-03463275: In clinical trials in healthy controls and patients with schizophrenia, common risks reported include fatigue, thirst, somnolence, insomnia, headache, akathisia, tremors, nausea, increased urination, gastrointestinal disturbances including abdominal pain, nausea, constipation and diarrhea. Visual disturbances include the brightening of vision and perception of flashing lights and one patient with schizophrenia also reported blurring of vision. These were transient and not associated with any visual changes on further testing. Palpitations, tachycardia and hypotension (in one subject) were noted, but resolved without any medical intervention. One patient with schizophrenia had ventricular systoles and was noted to have a 20 msec increase in QTc interval. Finally, 2 subjects with schizophrenia had elevations in AST/ALT levels and one subject had elevated glucose level attributable to treatment with PF-03463275. Thorough screening and frequent assessments for adverse events (See Section XII) are in place to mitigate the risks. Certain foods and medications may interfere with the metabolism of PF-03463275 and result in very low or high drug levels. This may result in loss of efficacy or increased risk of adverse events. Subjects will be advised to avoid these medications and this will be confirmed at each study visit. These include: Drugs or foods/food products that inhibit CYP2D6 and CYP3A4 (e.g., quinidine, fluoxetine, paroxetine, amiodarone, cimetidine, clarithromycin, diltiazem, erythromycin, fluvoxamine, nefazodone, nelfinavir, ritonavir, troleandomycin, and verapamil, indinavir, itraconazole, ketoconazole, mibefradil, grapefruit and grapefruit juice). Drugs that induce CYP3A4 will also be excluded (for e.g., carbamazepine, phenytoin, phenobarbital, rifampin and rifabutin).

- 4. Long Term Potentiation Event Related Potentials: There are minimal risks associated with EEG/ERP recording. Traditionally, scalp abrasion has been used to improve signal impedance at the electrode site. The EEG/ERP system used in this laboratory is a high-impedance system and does not require scalp abrasion to obtain clean recording. A conductive gel is applied, which can be easily washed out of the subject's hair with warm water. A shower facility for hair washing and sterile linens are available in the laboratory. Electrode caps and sensors will be washed and sterilized between subjects to minimize the risk of transmitting infection.
- 5. **Cognitive Remediation:** There are no known physical risks associated with computer-based cognitive remediation. Fatigue and frustration during training are possible. If this occurs, subjects will be encouraged to take breaks, during which they can drink coffee or halt training for the day. Research staff will monitor subjects during training and may advise them to seek further treatment if symptoms worsen as a result of participation in the study.
  - a. Reduction of Risk: Subjects will be encouraged to maintain the pace of cognitive exercises and not to be worried about performance. They will be encouraged and reassured. If they need a break, they will be encouraged to take one and return. The cognitive remediation in this study allows for a flexible training schedule. If subjects appear to be getting distressed, they will have the opportunity to talk with one of the investigators and may even be asked to return for the session. At the Learning Based recovery center, [name] has enormous experience using cognitive remediation in patients with schizophrenia. Overall, this is tolerated very well and subjects usually find it very motivating and helpful. Some of the behavioral questions may be distressing to patients. This risk is discussed in the consent process and subjects will be reminded that they can stop at any time and can choose not to answer. In case of marked worsening of symptoms, they will be evaluated by a psychiatrist, referred to their usual outpatient treater. Further, if indicated they may be escorted to the ER for an evaluation or admission as clinically indicated.

#### **SAFETY**

Data and Safety Monitoring Plan: The safety data is reviewed after every test day, during weekly research team meetings, and will be suspended or modified if indicated.

Adverse events will be graded in severity as follows:

- **0** No adverse event or within normal limits
- **1** Mild adverse event
- 2 Moderate adverse event
- 3 Severe adverse event resulting in hospitalization or prolongation of existing hospitalization, a persistent or significant disability/incapacity, or a congenital anomaly/birth defect.
- 4 Life-threatening or disabling adverse event
- **5** Fatal adverse event

The expected effects of Ketamine will not be recorded as adverse events.

Adverse events > level 3 will be reported to the IRB within 24 hours. Other adverse events will be reported to the IRB in a timely manner, using the following predefined causal relationships:

- i. Definite: Adverse event(s) will clearly be related to investigational agent(s) or other intervention
- ii. Probable: Adverse event(s) will likely be related to investigational agent(s)
- iii. Possible: Adverse event(s) may be related to investigational agent(s)
- iv. Unlikely: Adverse event(s) will doubtfully be related to investigational agent(s)
- v. Unrelated: Adverse event(s) will clearly not be related to the investigational agents(s)

Serious, unanticipated and related adverse events will be reported to VA-HSS and Yale HIC.

Informed Consent: Subjects who meet entry criteria mentioned above will be invited to meet with the research staff, who will fully explain risks and procedures as outlined in the consent form. After reviewing this information and answering questions, informed consent will be obtained from all subjects. The informed consent form (see attached), which will be given to the participating subjects, explains all the information pertaining to this study such as the objectives of the study, the procedures, risks and benefits, confidentiality, safety measurements, payment and other aspects of the study. Understanding of the information prior to obtaining consent is verified using a questionnaire (see attached).

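### The adverse-event scale merges severity with seriousness, so some severe events have no level and level 3 hospitalizations fall outside the 24-hour IRB rule

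*Protocol*

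**What the plan says.** The Data and Safety Monitoring Plan, under Safety in the protocol, introduces its scale with the words "Adverse events will be graded in severity as follows". Level 0 is no event and level 1 is mild. Level 2 reads only "Moderate adverse event". Level 3 is "Severe adverse event resulting in hospitalization or prolongation of existing hospitalization, a persistent or significant disability/incapacity, or a congenital anomaly/birth defect". Level 4 is "Life-threatening or disabling adverse event", and level 5 is fatal.

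Three reporting sentences follow:

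- The rule with a fixed deadline: "Adverse events > level 3 will be reported to the IRB within 24 hours".
- The rule for all remaining events, which sets no deadline: "Other adverse events will be reported to the IRB in a timely manner, using the following predefined causal relationships".
- After the list of causal categories: "Serious, unanticipated and related adverse events will be reported to VA-HSS and Yale HIC".

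The protocol does not define what makes an event serious. The SAP does not mention adverse events.

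**The concern.** Severity is how intense an event is. Seriousness is what the event led to. Levels 1 and 2 are pure intensity grades. Level 3 then adds a condition on outcome, so the scale changes meaning partway up. This raises two problems.

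The first is grading. A severe event that does not meet the outcome condition, and is not bad enough for level 4, has nowhere to go. Such events are foreseeable here. Under Risks and Benefits, item 3, the protocol reports from previous trials that "Finally, 2 subjects with schizophrenia had elevations in AST/ALT levels", and that one patient had a 20 msec QTc increase. Table 1 schedules the metabolic panel, ECG and movement exam at weeks 0, 2, 4, 8, 10 and 12, so a marked change could well be found at a routine visit without any admission. If raters place such events differently, the severity record is unreliable for the team's own safety review and for any later comparison of 40 mg, 60 mg and placebo.

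The second is reporting. The usual seriousness outcomes appear only inside the severity levels, and the 24-hour rule is keyed to those levels. A faulty scale therefore carries over into the timing of IRB reports.

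**Working it through.** No figure in the plan bears on this point and no arithmetic applies. The check treats the level definitions as a classification rule and runs types of event through it.

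**Inputs (protocol, Safety):** level 2 is moderate with no further criterion. Level 3 is severe and resulting in at least one of hospitalization or its prolongation, persistent or significant disability or incapacity, or birth defect. Level 4 is life-threatening or disabling, with no admission required. Level 5 is fatal. The 24-hour rule covers levels strictly above 3, that is, 4 and 5.

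| Event | Level as written | IRB within 24 hours? |
|---|---|---|
| Severe; no admission, disability or birth defect; not life-threatening or fatal (e.g. marked AST/ALT or QTc change at a scheduled visit) | None: above 2, fails the condition of 3, does not reach 4 | No, whether 2 or 3 is chosen |
| Severe; leads to admission; not life-threatening or disabling | 3 | No |
| Severe; significant disability, no admission | 3 or 4 | Depends on which is chosen |
| Moderate intensity; short admission | Unclear: the word severe excludes 3, the outcome points to 3, and 2 remains open | No, on either choice |
| Life-threatening; no admission | 4 | Yes |

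**Row 1** is the gap. Nothing else in the protocol or SAP defines severity or gives a default for such an event.

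**Row 2** shows that a severe event causing hospitalization falls under the sentence with no fixed time limit.

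**Row 3** shows that the overlap on disability sits exactly on the 24-hour threshold. The same event is reported within 24 hours, or without a deadline, according to which of two matching levels the rater picks.

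**The separate route for serious events** does not close these openings. It requires an event to be serious, unanticipated and related all at once, it states no time limit, and it leaves serious undefined.

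**The case against.** The strongest reply is that the gap is a narrow drafting matter with little consequence. Much of this is correct.

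- A reader might infer that an event in the gap must be graded as moderate. The documents state no default, and a rater could equally choose level 3 on the word severe. What can be said is that grading is undefined and may vary.
- A reader might take outpatient management as the test. It is not. Admission is only one of the level 3 outcomes, and level 4 needs none. Incapacitating akathisia in an outpatient, for example, arguably fits level 3 or level 4. That is overlap, not a missing level.
- A reader might infer that a modest event with a short admission is forced up to level 3. If level 3 requires severe intensity, which is the reading that creates the gap, it is not.
- For an event in the gap, the choice between levels 2 and 3 triggers no different action in the plan. Neither level meets the 24-hour rule, and no stopping or modification rule is tied to level 3.
- The safety review covers safety data generally, after each test day and weekly. A marked laboratory or ECG value need not be hidden by its grade.
- The risks text calls none of its listed events severe, and many are ordinary reported symptoms.

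These points limit the consequences. They do not supply a level for the events in the first row of the table, and they do not answer the disability overlap, the undefined term or the missing deadline for level 3 hospitalizations.

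**Conclusion.** The concern holds in this form. The scale mixes intensity with outcome, so a definable class of severe events has no level. The same mixing leaves disability in two levels, serious without a definition, and level 3 hospitalizations with no fixed IRB deadline. This is a fault in a rule the protocol states, and it should be corrected.

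Its size cannot be given as a number. A reader might infer that most severe events in this trial are affected, but the documents contain no counts to support that. A reader might also infer that planned severity tables by dose would hide drug effects. The SAP plans no adverse-event tables, so any effect on such tables is conditional on someone producing them.

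Two assumptions matter. The reporting part takes the 24-hour threshold as strictly above level 3, as printed. If level 3 was meant to be included, the missing deadline for level 3 hospitalizations falls away, but the grading gap remains. Also, the drug-risk item refers to a Section XII for adverse-event assessments, and no section with that number stands in the protocol text available. If it defines severity, the levels should be checked against it.

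**What to change.** 1. Define level 3 by intensity alone, for example an event that prevents usual activity or a marked laboratory or ECG change, whatever its outcome. The investigators would set what counts as marked.
2. Add a separate yes/no field for seriousness, with its criteria listed: hospitalization or its prolongation, disability, birth defect, life-threatening, death. The same list then defines serious for the VA-HSS and Yale HIC route.
3. Reconcile disability between levels 3 and 4, so that one event cannot satisfy both.
4. Key expedited IRB reporting to the seriousness field instead of the severity level.
5. If adverse events are summarized by treatment, show severity and seriousness separately.

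The cost is a few lines of protocol text and one field on the adverse-event form. Somewhat more events will be recorded as severe, and somewhat more expedited reports will be made.

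### Do the overlapping level 3 and level 4 definitions, together with the 24-hour IRB threshold, require a change to the safety-reporting rule?

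*Protocol*

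**What the plan says.** The adverse event scale is in the protocol's Safety section, under the Data and Safety Monitoring Plan. Level 3 covers a "Severe adverse event resulting in hospitalization or prolongation of existing hospitalization" and also "a persistent or significant disability/incapacity, or a congenital anomaly/birth defect". Level 4 is a "Life-threatening or disabling adverse event", and level 5 is fatal.

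Three reporting statements follow the scale:

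- The expedited rule reads: "Adverse events > level 3 will be reported to the IRB within 24 hours".
- The rule for everything below that threshold reads: "Other adverse events will be reported to the IRB in a timely manner", with the causal category attached. No number of hours or days is given.
- A separate rule names two committees: "Serious, unanticipated and related adverse events will be reported to VA-HSS and Yale HIC". This also carries no time limit.

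The same section describes internal oversight: "The safety data is reviewed after every test day, during weekly research team meetings". The SAP does not mention adverse events or their grades.

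**The concern.** Two features look wrong when read together. First, the scale does not separate its levels cleanly. A disabling event meets the wording of level 3 and of level 4, and no rule says which applies, so two raters could grade the same event differently and both follow the protocol.

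Second, the expedited-reporting cut falls exactly on that boundary. Read as printed, only levels 4 and 5 go to the IRB within 24 hours. A hospitalisation, which many readers would expect to be expedited, then falls under the untimed rule. A disabling event would be inside or outside the 24-hour rule depending on the rater.

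The situation is foreseeable. Under Risks and Benefits, the cognitive remediation item anticipates emergency evaluation or admission if symptoms worsen markedly. If the concern held, staff would not know whether such an admission has a deadline, and oversight of participant safety could be slower than intended.

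**Working it through.** The plan states no figure here to reproduce, and no formula applies. The check is to apply each reading of the threshold to each kind of event the scale names.

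| Event | Level | Sign read as strictly above 3 | Sign read as 3 or above |
|---|---|---|---|
| Mild or moderate | 1 or 2 | no fixed time | no fixed time |
| Hospitalisation, neither life-threatening nor disabling | 3 | no fixed time | 24 hours |
| Congenital anomaly | 3 | no fixed time | 24 hours |
| Disabling, graded 3 | 3 | no fixed time | 24 hours |
| Disabling, graded 4 | 4 | 24 hours | 24 hours |
| Life-threatening or fatal | 4 or 5 | 24 hours | 24 hours |

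1. **Overlap.** The two disability rows differ only under the strict reading. Under the inclusive reading both carry 24 hours, so the overlap has no reporting consequence. Even under the strict reading, a rater who assigns the highest level whose definition is met would grade a disabling event 4, and the two rows become one. The protocol does not state that convention, but it is an ordinary way to resolve such a scale.

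2. **Threshold.** The readings differ only for level 3. The text was machine-read from PDF, and an inclusive sign can lose its bar in that process. No other sentence in the protocol or SAP restates the threshold, so the text cannot decide between the readings.

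3. **What happens to a level 3 event in the worst case.** It is still reported to the IRB, without a stated time. If it is also serious, unanticipated and related, it goes to the two named committees as well. It also comes before the team's review after test days and at weekly meetings.

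4. **Contact with participants.** The Economic Considerations section pays \$5 per compliance phone visit, up to \$350. That is 350 / 5 = 70 visits, or 70 / 14 = 5 per week if spread evenly over the 14 weeks that Table 1 numbers from first dosing. It also plans about 40 training sessions over about 8 weeks, or 40 / 8 = 5 per week. These contacts are not described as adverse event checks, but they make it unlikely that an admission would go unnoticed for long.

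5. **Analysis.** The SAP fits a mixed model to each dependent measure with dose, visit, their interaction and period. Severity grade does not enter, so no specified estimate, test or error rate changes under either reading or either grading of a disabling event.

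**The case for a change.** The strongest opposing case is that the overlap is plain wording and cannot be blamed on PDF reading. It could affect any later tabulation of events by severity, even where reporting times are the same. Nothing else in the Safety section closes the deadline gap under the strict reading: the rule for the two committees requires three conditions at once and gives no time, and internal review is not a report to the IRB. Correcting it would take one sentence and one line of the scale.

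The overlap does stand, and so does the point that the other rules do not supply a deadline. Neither makes the plan defective. A strict threshold with an untimed rule for the rest is a possible choice, and nothing in the documents shows it to be an error.

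The delay cannot be sized either. The weekly meeting interval describes internal review, not the time to an IRB report, so it cannot be set against 24 hours. The documents give no hospitalisation rate, so any count of affected events would only repeat an assumed rate. Entry requires no psychiatric hospitalisation in the past 3 months, which suggests such events may be few.

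Nor can the absence of a deadline elsewhere be assumed. The drug-risk paragraph under Risks and Benefits says "Thorough screening and frequent assessments for adverse events (See Section XII) are in place to mitigate the risks". No section with that number is in the supplied text, which also refers to a first sub-study, ketamine and healthy controls. It therefore seems to come from a larger document that may hold further reporting detail.

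**Conclusion.** No change to the plan is needed. Disability is listed at two levels, which is a slip in wording. It affects a reporting deadline only if the threshold is strict and the rater chooses the lower level. The threshold itself is ambiguous in the supplied text, and one plausible reading removes the reporting issue altogether.

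The effect on the efficacy analysis is nil. The effect on safety reporting is confined to when level 3 events reach the IRB, not whether they do, and its size cannot be estimated from the documents.

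This rests on three assumptions: that the sign may have been altered in PDF reading, that staff graded and reported events sensibly where the wording overlaps, and that the SAP's date (5/28/2021) and past tense mean data collection was over. If the last holds, amending the protocol sentence would gain nothing. The most that could be useful is a line in the study report saying which threshold was applied and how disabling events were graded. This review takes no position on which reporting threshold is right.

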# **Economic Considerations: Sub-study 2:**

Sub-study 2Visit	Amount	Method
Screening Visit 1	\$25	Cash
Screening Visit 2	\$25	Cash
Baseline	\$75	Cash
Period 1		
Week 1	\$75	Cash
Week 2	\$100	Debit Card
Cog Rem-Session 5	\$20	Debit Card
Week 3	\$100	Debit Card
Cog Rem- Session 10	\$30	Debit Card
Week 4	\$100	Debit Card
Cog Rem- Session 15	\$40	Debit Card
Week 5	\$100	Debit Card
Cog Rem- Session 20	\$50	Debit Card
Washout Week 1	\$20	Debit Card
Washout Week 2	\$20	Debit Card
Period 2		
Week 9	\$100	Debit Card
Cog Rem- Session 25	\$60	Debit Card
Week 10	\$100	Debit Card
Cog Rem- Session 30	\$70	Debit Card
Week 11	\$100	Debit Card
Cog Rem- Session 35	\$80	Debit Card
Week 12	\$100	Debit Card
Cog Rem- Session 40	\$90	Debit Card
Follow- Up	\$75	Debit Card

Subjects will be compensated up to \$50 for completion of screening processes, which will take place at the VACHS and Yale University. These aforesaid processes will take approximately 8 hours and may take multiple visits. In this case, the total amount of the screening will be split between the visits. For example, the subject will be paid \$25 for the first visit and \$25 at the subsequent screening.

Subjects can earn up to \$1, 555 for completion of all study procedures. Participants will receive compensation only for study visits that are attended. Payments for screening, baseline and week 1 will be made via cash. All other visits will be paid via debit card unless otherwise requested by the subject or his/her conservator, and agreed upon by the P.I.

To encourage participation in cognitive training, additional incentive payments will be dispensed for cognitive training activity, amounting up to \$440. Training will be administered over approximately 8 weeks, during which you will be asked to complete approximately 5 sessions per week, for a total of about 40 sessions. Incentive payments will be earned in blocks of 5 sessions, and dispensed according to the schedule outlined in the Economic Considerations Table. A maximum of 5 sessions can be completed each week, and no additional incentive payments will be made after 40 training sessions. A partial payment may be made at the final training session based on the percentage of training you complete toward the next payment point.

In addition to the compensation for each in-person visit, subjects will be compensated \$5 for completing each compliance monitoring or CAROMA visit by phone. CAROMA visits will only be completed on weekdays that the research clinic is open. Subjects may earn up to \$350 dollars for completing all possible CAROMA visits.

TABLE 1:Substudy 2 Procedures																		
	Screen		eline eeks)	Period 1 (5 weeks)					Washout (3 weeks)			Follow - Up						
Week	Screen	-2	-1	0	1	2	3	4	5	6	7	8	9	10	11	12	13	14
Day		-14	-7	0	7	14	21	28	35	42	49	56	63	70	77	84	91	98
SCID	Х																	
WTAR	х																	
Psych Evaluation	х																	
Physical	Х																	
Genotyping	Х																	
Randomizat ion				х								х						
PF v Placebo				х	х	х	х	Х	х			х	х	х	х	х	х	
CR					х	х	х	х	Х				х	х	х	х	х	
PANSS				х		Х		х				х		Х		х		
SGI				х		Х		Х	Х			х		х		х	Х	
PAOFI				Х		Х		Х	Х			Х		Х		х	Х	
Movement Exam				х		х		х				х		х		х		
MCCB		Х								Х								Х
LTP				Х					Х			Х					Х	
PK				Х	Х	Х	Х	Х	Х			Х	Х	Х	Х	Х	Х	
BDNF				х														
СВС	Х			х		Х		Х				х		х		Х		
CMP	Х			х		Х		х				х		Х		Х		
ECG	х			х		Х		х				Х		Х		Х		
Utox	х	Х	Х	Х		х		Х		Х	Х	Х		Х		Х		

SCID: Structured Clinical Interview for DSM IV; WTAR: Wechsler Test of Adult Reading; CBC: Complete Blood Count; CMP: Comprehensive Metabolic Panel; ECG: Electrocardiogram; Utox: Urine Toxicology screen; CR: Cognitive Remediation; PANSS: Positive and Negative Syndrome Scale; Sensory Gating Inventory; PAOFI: Patient Assessment of Own Functioning Inventory; LTP: Long Term Potentiation; BDNF: Brain Derived Neurotrophic Factor. Per P.I. discretion, study procedures may be repeated, and the duration of participation may be extended to account for scheduling conflicts and extenuating circumstances. Thus, the number of weeks listed per period may vary.

